Study Title: Specialized Community Disease Management to Reduce Substance Use and Hospital Readmissions

NCT Number: NCT02059005

Document Date: March 4, 2016

Treatment Research Institute—Institutional Review Board**SUMMARY OF HUMAN SUBJECTS RESEARCH PROTOCOL**

Please address all applicable points to create a complete and succinct synopsis of the protocol. Use language, insofar as is possible, that can be understood by an external, non-scientist layperson, and provide meanings for all acronyms used. **Form must be typewritten.**

(Maintain subheadings in body of text.)

Title of project: Specialized Community Disease Management to Reduce Substance Use and Hospital Readmissions

Funding Source and Funding Dates (Start and End Dates): Patient Centered Outcomes Research Institute (PCORI), 3/1/2014 – 2/28/2017

Name, address, agency, and phone number of principal investigator:

[name]., Senior Scientist
Treatment Research Institute
[name]
[name]
[name]
[contact] x 128

1. Introduction and rationale for study

Hospitalized patients with substance use disorders (SUDs) face significant complications in their medical care. They are more likely to be discharged against medical advice, rehospitalized after discharge, and experience personal chaos and reduced family support. Rapid rehospitalization (RRH) is receiving increasing focus as a healthcare quality issue, and the Centers for Medicare and Medicaid Services (CMS) have instituted penalties on hospitals where there is a significant rate of RRH within 30 days. Currently, hospital penalties are adjudicated based on the RRH rates of three conditions: congestive heart failure, acute myocardial infarction, and pneumonia. Due in large part to these Medicaid penalties, hospital systems are moving quickly to implement hospital-based and community disease management strategies to help patients transition post-discharge. However, few hospitals provide specialized follow-up for discharged patients with SUDs. Inpatients with substance use disorders may not be served well by existing disease management programs intended to reduce rehospitalizations because the programs do not attend to their SUD and related psychosocial problems (isolation, unstable housing, mental illness, HIV infection, etc.).

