Specialized Community Disease Management (SCDM): The SCDM intervention will last for 90 days and will be administered by a Licensed Clinical Social Worker (LCSW) functioning as a Behavioral Health Consultant (BHC) trained in evidence-based brief intervention and brief treatment approaches. After enrollment in the study, the BHC will conduct 1-2 brief intervention sessions at bedside. If a participant is discharged from the hospital before the BHC is able to conduct an initial brief intervention session, the BHC will contact the participant in the community and complete the initial session within one week after the participant's discharge from the hospital. These sessions will last 20-40 minutes each, and the BHC will employ motivational enhancement treatment (MET) with targeted behavioral strategies to create a problem-centered, flexible intervention strategy for patients at various levels of readiness to change. Patients are provided with direct normative feedback based on their use level and encouraged to quit or cut down. In most cases, this will include a discussion of the patient's past efforts to quit and previous treatment attempts. The BHC will negotiate an open, modifiable goal regarding how patients would like to handle their substance use. This approach is flexible as patients who would not consider treatment or working towards abstinence can often still connect with the BHC around less stringent goals (cutting down / harm reduction). The BHC's feedback will emphasize the importance of considering and engaging in treatment.

If a patient is willing to enter treatment, the BHC will work with the hospital discharge planning team to find suitable referrals and work to secure a place in an appropriate facility. Additionally, the BHCs will explore the participant's risk for contracting HIV and determine whether the patient has been tested; participants at risk who have not been tested recently will be encouraged to be tested while an inpatient. The BHC will provide the participant with various health communication materials from our Brief Intervention Toolkit. Finally, while still inpatient, the BHC will orient the participant to the procedures of the telephone-based follow-up calls and introduce the peer CHW, who can follow-up on treatment and recovery matters with participants (see below for the full description of the CHW's role).

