Non-Study Medical and Other Services (NSMOS): This questionnaire was adapted from the Treatment Services Review (McLellan et al., 1992) for patients in medical settings. The NSMOS counts substance abuse treatment, medical services, visits to medical offices, hospitalizations, and emergency room visits received that were not a part of the assigned treatment. *Administered at 0,3,6 months. Brief version administered at 1 and 2 months.*

Temple Hospital Utilization Review: TUH conducts utilization reviews on all patients discharged for the targeted medical conditions to determine whether patients experience rehospitalization and use the emergency room. This data is pulled through a pre-written algorithm which can be adjusted to pull all inpatient and ER encounters over a six-month period. The TUH Institute for Population Health will supply this data for study participants.

HIV Risk Assessment (HIV-RA): The HIV Risk Assessment provides a brief self-report measure of HIV testing history and sexual risk and uses the preceding three months as the time interval of interest. The HIV-RA was developed [name], and [name], experts in the field of HIV risk behaviors. *Administered at 0,3,6 months.*

Addiction Severity Index-6th Edition Modified Version (ASI6-Modified). The ASI is a multi-dimensional interview used to measure the substance use, health, and social problems of those with alcohol and other drug problems, both at admission to treatment and subsequently at follow-up contacts (McLellan et al., 1992; McLellan et al., 1980). We are using an abbreviated version of the ASI-6 that eliminates many of the items that do not contribute to our primary hypotheses and takes approximately 20 minutes to complete. We will use only the ASI domains for medical, drug use, alcohol use, and psychological status for covariate analysis. The ASI-6 produces Recent Status Scores in each of these four areas, which have demonstrated high levels of inter-rater, test-retest, and concurrent reliability (Cacciola et al., 2011). *Administered at 0,3,6 months.*

Healthy Days Symptoms: The Healthy Days Symptoms Module (Newschaffer, 1998) was taken from the CDC's Health-Related Quality of Life Survey, which is part of the State-based Behavioral Risk Factor Surveillance System (BRFSS). This module measures the number of days over the past month that a patient was affected by symptoms such as pain and anxiety, as well as the number of healthy days. *Administered at 0,3,6 months.*

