engaged in the study for only a 6-month period, we will not report any AEs that are discovered via chart data collection that occurred outside of the participant's period of active participation in the study. However, we will report any AEs discovered through chart data collection if they occurred during the participant's period of active engagement in the study and were not previously reported. The period of active engagement in the study will be defined as beginning with the date of consent and ending six months after the date of consent.

13. If this study is a chart review, indicate the time frame of data to be collected (from when to when). Also, will the data be collected anonymously (meaning that only aggregate data will be collected, and there will be no names or codes maintained to match the data with the original files)?

We will collect data from participants' medical charts at TUH as part of this study. This information will include the patient's name, health insurance status, hospitalizations, emergency room visits, diagnoses, medications, and results of urine drug tests at TUH. We will collect this information beginning on the date two years prior to the participant's study enrollment date and ending on the date three years after their study enrollment date. The data will not be collected anonymously, as we will need to link the chart data to specific participants in order to determine study outcomes. However, we will de-identify all research data collected from the charts; this data will be linked and stored under the participants' research identification numbers. All chart data will be provided to TRI by TUH.

14. Children, defined as individuals under the age of 21, must be considered for potential enrollment in every study as subjects unless there are scientific or ethical reasons for excluding them. See below for the permissible exclusionary circumstances listed in the NIH Policy. If no exclusion applies: 1) discuss your plan for the inclusion of children; 2) justify the age range of children to be enrolled; 3) indicate the expertise of the research team with regard to children; 4) describe the facilities for the children; 5) indicate the number of children to be enrolled to give sufficient power for meaningful analysis; 6) describe how the assent process for children 7 to 17 years of age will be carried out.

Justify your exclusion based on one of the exclusionary circumstances listed:

- The research topic is irrelevant for children

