Study Title: Specialized Community Disease Management to Reduce Substance Use and Hospital Readmissions

NCT Number: NCT02059005

Document Date: June 30, 2017

Data Analysis Plan

Analyses will compare outcomes for the TAU and SCDM groups. We will employ remedial measures such as power transformations when necessary. We will confirm that the groups do not differ at baseline on relevant background variables using t-tests for continuous variables and chi-square tests for discrete or ordinal responses. The randomization process should minimize the need for the inclusion of covariates to reduce bias in the treatment comparisons ¹. However, relevant covariates will be considered for inclusion in the analyses to improve the precision of estimation of the effects ².

Power Analysis. The power analysis for the primary hypothesis was conducted following the recommendations of Diggle et al. ³ for mixed effects models. Using a two-sided alpha of .05, an estimated intraclass correlation of .7 between the repeated measurements, and a 15% attrition rate by month 6, we will have 85% power to detect a moderate effect of the intervention ($d = .4$) with a sample size of 111 patients in each group (222 altogether).

Primary hypothesis: Patients assigned to the SCDM condition will report significantly fewer days of substance use than patients assigned to TAU. Using TLFB data, we will create a variable for days of any substance use by combining all drug types and alcohol. Urine samples collected at months 3 and 6 will be used to confirm reports of drug use. Provided that the rate of disagreement between urine results and self-report is acceptable (below 15%), we will analyze days of substance use as a unitary variable. A linear mixed effects model ² will be used to examine days of self-reported drug use in the past 30 days at each follow-up assessment. Mixed effects models have advantages over conventional repeated measures methods in that they allow for missing observations, accommodate measurements made at different time points, provide greater flexibility in modeling the variance-covariance matrix, and permit the estimation of group and random subject-specific effects. The model will include terms for condition, assessment point, and their interaction along with any necessary covariates including the number of days of use reported at the baseline. The analysis will be conducted using

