SAS's PROC MIXED. Should the rate of disagreement between urine and self-report exceed acceptable standards; we will analyze the urine results as the primary outcome. However, the literature indicates that self-report of substance use is generally quite accurate ^{4,5}.

Secondary hypothesis (a): Patients assigned to the SCDM condition will exhibit greater reductions in days of hospitalization and acute emergency care over the six-month period than patients assigned to TAU. A linear mixed effects model ² will be used to compare participants in the two groups on the days of inpatient and ED utilization in the past 90 days at the 3 and 6-month follow-up assessments. The model will be similar to that outlined for the primary hypothesis.

Secondary hypothesis (b): Patients assigned to the SCDM condition will demonstrate higher rates of engagement in substance abuse treatment than patients assigned to TAU. A linear mixed effects model ² will be used to compare patients in the two groups on the number of treatment sessions attended in the past 90 days at the 3 and 6-month assessments, similar to that outlined for the primary hypothesis.

Exploratory hypothesis: Patients randomized to SCDM will demonstrate a) reduced HIV transmission risk behaviors, and b) greater incidence of HIV testing over the 6 month follow-up than patients randomized to TAU. Secondary efficacy analyses will be conducted to examine the effects of the intervention on HIV related behaviors. A linear mixed effects model ² will be used to compare the two groups' RAB scores (i.e., total, sex, drug) at months 3 and 6. The baseline response will be included as a covariate. A logistic regression model will be employed to test differences in incidences of testing.

References:

1. Tabachnik B, & Fidell, L.S. *Using multivariate statistics*. Boston, Massachusetts: Allyn and Bacon; 1994.

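### The HIV-testing model states no restriction by HIV status and names no baseline covariate, which gives up some precision on an exploratory outcome

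*SAP*

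**What the plan says.** The SAP's Exploratory hypothesis predicts a higher incidence of HIV testing over six months under SCDM. The whole analysis is one sentence: "A logistic regression model will be employed to test differences in incidences of testing". No denominator, covariate or handling of HIV status follows. In the same paragraph a baseline covariate is named for the risk-behaviour scores, but not for testing.

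Four places in the protocol bear on this:

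- Item 1 lists the problems that accompany substance use disorders in these inpatients: "isolation, unstable housing, mental illness, HIV infection, etc". It gives no prevalence.
- The exclusion criteria in item 9 do not mention HIV infection.
- Item 6, under SCDM, describes the prompt: "participants at risk who have not been tested recently will be encouraged to be tested while an inpatient".
- Item 7 describes the HIV-RA, given at 0, 3 and 6 months, as a "brief self-report measure of HIV testing history and sexual risk". Item 13 adds hospital chart data, including "hospitalizations, emergency room visits, diagnoses, medications, and results of urine drug tests at TUH", from two years before enrolment to three years after.

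**The concern.** The people to whom the prompt is addressed and the people in the comparison are not the same. A participant already known to be HIV-positive is not a candidate for a prompted test, so the intervention cannot change that participant's outcome. Each such participant adds to the denominator in both arms and nothing to the difference. Recently tested participants are also outside the prompt's target, and a record of prior testing is the obvious baseline predictor of later testing. The model names neither a restriction nor that predictor.

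At stake are the precision of this one comparison and the meaning of the reported rate, which would describe a mixture of people who could and could not be prompted. Because the denominator is unstated, it could also be chosen after the data are seen.

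**Working it through.** **Step 1. The plan's own power figure.** Inputs from the SAP's Power Analysis: "Using a two-sided alpha of .05", "an estimated intraclass correlation of .7 between the repeated measurements", "a 15% attrition rate by month 6", d = 0.4 and 111 per group. There are two follow-up interviews, at months 3 and 6 (protocol item 6).

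- Variance factor for the mean of two measurements: (1 + 0.7)/2 = 0.85.
- Evaluable per arm: 111 × (1 − 0.15) = 94.35.
- Standard error: √(2 × 0.85/94.35) = 0.1342.
- 0.4/0.1342 = 2.980, and power = Φ(2.980 − 1.960) = 84.6%, against 85% stated.

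The figure reproduces. It concerns days of substance use only; the documents give no power for HIV testing.

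**Step 2. Set-up for HIV testing.** Let h be the share known to be HIV-positive at enrolment, and p0 and p1 the testing rates among everyone else in TAU and SCDM. All three are assumptions. So is the coding of known positives as having no new test, and so is applying the 15% attrition and two-sided 0.05 to this outcome.

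- Everyone included: rates a = (1 − h)p0 and b = (1 − h)p1, with n = 94.35 per arm.
- Restricted: rates a = p0 and b = p1, with n = 94.35(1 − h) per arm.
- Power = Φ((b − a)/SE − 1.960), with SE = √([a(1 − a) + b(1 − b)]/n).

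**Step 3. One case in full: h = 10%, 30% versus 50%.**

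- Included: 27% versus 45%. SE = √((0.1971 + 0.2475)/94.35) = 0.0686; 0.18/0.0686 = 2.622; power 74.6%.
- Restricted: n = 84.9. SE = √((0.21 + 0.25)/84.9) = 0.0736; 0.20/0.0736 = 2.717; power 77.6%.

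**Step 4. Range of h at 30% versus 50%** (odds ratio 2.33 when restricted).

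| h | Rates, everyone | Difference | Odds ratio, everyone | Power, everyone | Power, restricted |
|---|---|---|---|---|---|
| 5% | 28.5% vs 47.5% | 19 points | 2.27 | 78.3% | 79.7% |
| 10% | 27% vs 45% | 18 points | 2.21 | 74.6% | 77.6% |
| 20% | 24% vs 40% | 16 points | 2.11 | 66.7% | 72.6% |

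**Step 5. Sensitivity.**

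- *Other testing rates.* Over 10/25%, 20/40%, 30/50%, 40/60% and 60/80%, with h from 5% to 20%, restriction always gives the higher power. The gain runs from 0.5 points (10/25%, h = 5%) to about 17 points (60/80%, h = 20%). At 40/60% and h = 20%, power is 62.3% against 70.8%.
- *Variance formula.* A pooled variance lowers the Step 4 figures by about one point (77.1 vs 78.5, 73.5 vs 76.3, 65.6 vs 71.2) and leaves the pattern unchanged.
- *Coding.* Suppose 90% of known positives in both arms answer that they were tested. At h = 10% the rates become 0.27 + 0.09 = 36% and 0.45 + 0.09 = 54%. Power is then 71.5%, still below the restricted 77.6%. The direction does not depend on the no-new-test assumption here, though the size does.

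The gain from adjusting for baseline testing history is not quantified, because the documents do not say how strongly it predicts later testing.

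**The case against.** The strongest reply is that the SAP does not say known positives are kept. A reader might infer a deliberate decision to analyse everyone; the text supports only that no restriction is stated. That is right, and the point is confined to it. With nothing excluding anyone, a comparison of all randomized participants is still the natural reading.

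A reader might also infer that the comparison is biased. It is not: known HIV status at enrolment should be balanced by randomization, and the all-randomized contrast is valid for the enrolled population. Restriction targets a somewhat different population. That is a choice of estimand, made here for precision and relevance.

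Nor do the documents establish that known positives would be recorded as untested. The HIV-RA items and coding are not shown, so Step 5 varies this.

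It would be wrong to say that the SAP rules out a baseline covariate. Its opening paragraph allows relevant covariates in the analyses generally, so adjustment for testing history is permitted, though not specified.

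Finally, the proposed restriction does not fully match the prompt's target, since participants not at risk and those recently tested remain. The covariate deals with recent testing only in part. This objection stands as a limit on the remedy.

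**Conclusion.** The point holds as a modest loss of precision. It is not an error that threatens the trial's conclusions. Under 30% versus 50% testing, the power given up is about 1 to 3 points at 5–10% known positives and about 6 points at 20%. It becomes large only when the share of known positives and the testing rates are both high. All of this rests on assumed prevalence, testing rates and coding.

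A reader might infer that the stated 85% power is undermined. It is not, since that figure belongs to the primary hypothesis. A reader might also give the point the weight of a secondary hypothesis, because protocol item 2 lists HIV testing under Secondary Hypothesis (b). The later SAP, dated June 2017, makes it exploratory, and the priority of this point should follow that.

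**What to change.** In the SAP's Exploratory hypothesis, before the arms are compared:

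1. Include baseline HIV-testing history from the month-0 HIV-RA as a covariate in the logistic model. Protocol item 6 lets the Baseline Interview be finished up to a week later, so count only tests dated before enrolment.
2. Fit the model among participants not known to be HIV-positive at enrolment, using hospital chart diagnoses dated on or before enrolment plus any HIV-RA status item. The protocol does not name serostatus as an HIV-RA item, so confirm that it is captured. The date limit matters because the chart window runs to three years after enrolment.
3. Report the number excluded in each arm.
4. Give the all-randomized result as a sensitivity analysis.

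The cost is a few sentences in the SAP and a check of what the instrument and charts record; no new data collection is evident. The analysis set becomes slightly smaller, and some known positives diagnosed at other hospitals may be missed and so stay in the model.
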